4. STATISTICAL METHODOLOGY AND ANALYSES

4.1. Subject Disposition

The number and percentage of subjects will be tabulated for by Cohort, study drug, and overall:

- Screened Subjects (Signed Informed Consent)
- Randomized
- Randomized but not exposed to treatment
- Randomized and exposed to treatment

- Treatment Discontinuation
 - Subjects who completed treatment
 - Subjects who discontinued treatment early and the primary reasons for treatment discontinuation
- Study Discontinuation
 - Subjects who completed the study
 - Subjects who terminated the study early and the primary reasons for study discontinuation
 - Subjects with study ongoing at data cutoff

Subjects who were rescreened will be counted only once in the disposition summary based on the outcome of the last rescreening. If a subject failed multiple screenings, they will be counted only once as a screen failure. If a subject is randomized after multiple screenings they will be counted only once as a randomized subject.

4.2. Demographics and Baseline Characteristics

Demographic data and other baseline characteristics will be presented for all randomized subjects.

4.2.1. Demographics

The following demographic variables will be summarized by treatment group:

Age (years), calculated as the number of years between the date of birth and the date of signing the Informed Consent form.

- Age (years)
- Sex (Male or Female), Childbearing potential status for female.
- Race (White, Black or African American, Asian, American Indian or Alaska Native, Native Hawaiian or Other Pacific Islander, Other)
- Ethnicity (Hispanic or Latino, Not Hispanic or Latino)
- Height (cm)
- Weight (kg)
- BMI (kg/m^2)

4.2.2. Baseline Disease Characteristics

The following baseline characteristics will be summarized by treatment group.

- Duration of RA (Years)
- Rheumatoid factor (kIU/L)
- Anti-CCP (Positive, Negative)

• Stratification factor

- Cohorts 1 and 2: Prior failure, inadequate response, or intolerance to RA medication category (bDMARD vs. JAKi)
- Cohorts 3 and 4: Prior inadequate response to number of classes of advanced targeted therapy ($\leq 1 \text{ vs.} \geq 2$)

• ACR components

- TJC
- SJC
- PGA
- PhGA
- HAQ-DI
- CRP (mg/L)
- Pain VAS

DAS28-CRP

Please note that stratification factor (prior failure, inadequate response, or intolerance to RA medication category, bDMARD vs. JAKi) in Protocol Amendment 3 or earlier versions was changed to a new stratification factor (prior inadequate response to number of classes of advanced targeted therapy, ≤ 1 vs. ≥ 2) in Protocol Amendments 4 and 5 for Cohorts 3 and 4. The modified CRF will collect such information for subjects in Cohorts 3 and 4 who are randomized under either Protocol Amendment 3 or Protocol Amendments 4 and 5. The stratification will be derived per the information of prior inadequate response to RA medications for subjects who were randomized under Protocol Amendment 3, which will be reviewed in a blinded fashion before database lock.

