8.4. Randomization

All subjects who are eligible for study participation will be randomized on Day 1 prior to study drug administration. Each subject will be randomized to receive KPL-404 or placebo as per the randomization schedule prepared before the study by the Sponsor or designee. Randomization will be stratified by available documented evidence of prior inadequate response to ≤ 1 versus ≥ 2 classes of advanced targeted therapy (bDMARD or tsDMARD; e.g., TNF inhibitors, IL-6 receptor inhibitors, T-cell costimulatory inhibitors, anti-CD-20 antibodies, JAK inhibitors).

For Cohorts 1 and 2, subjects will be randomized 3:1, KPL-404 to placebo.

The overall randomization ratio in Cohort 3 is 1:1:1 (5 mg/kg q2wk, 5 mg/kg qwk, placebo). To maintain blinding, the placebo volume will be matched to the corresponding 5 mg/kg volume, and all subjects will be required to attend weekly visits through the treatment period.

The overall randomization ratio in Cohort 4 is 3:2 KPL-404 (600 mg loading dose at baseline followed by maintenance dosing 400 mg q4wk at Week 4 and Week 8) to matched placebo (equivalent volume; SC q4wk; loading dose at baseline followed by maintenance dose at Week 4 and Week 8).

An Interactive Response Technology (IRT) system will issue a unique randomization code to each subject, which will assign the treatment to the subject. The study drug will be assigned, prepared, and administered according to instructions in the Pharmacy Manual.

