11.4.2. Analysis Methods

For efficacy analysis, a 2-sided type 1 error rate of 0.05 will be used, if applicable.

For Cohorts 1 and 2, only descriptive statistics and listings will be produced for all efficacy parameters. No formal statistical testing for efficacy will be performed.

For Cohorts 3 and 4, an analysis of covariance (ANCOVA) model will be used to compare the change from baseline in DAS28-CRP at Week 12 for each of the KPL-404 dose groups and placebo. Baseline and randomization stratification factor will be included as covariates in the ANCOVA model. No testing between the two KPL-404 dose groups in Cohort 3 will be conducted. ACR response rates at Week 12 between each of the KPL-404 dose groups and placebo will be compared using Cochran-Mantel- Haenszel (CMH) test adjusted by stratification factor. In addition, logistic regression models may be used including key baseline characteristics as covariates in addition to the treatment. Details will be specified in the SAP.

Baseline is defined as the last non-missing value on or before Day 1.

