4.6.2. Analyses of Primary Efficacy Endpoint

The primary analysis for the efficacy endpoints will be based on the mITT population.

The following null hypothesis (H0) and alternative hypothesis (H1) will be tested for each KPL-404 dose against placebo:

- H0: No treatment difference between KPL-404 and placebo.
- H1: There is a treatment difference between KPL-404 and placebo.

The primary estimand for the primary endpoint is defined in Table 1, using the hypothetical strategy.

The intercurrent event that is deemed to have an impact on the interpretation of the variable of interest is treatment discontinuation or using any rescue medications. Data will be set to missing values after occurrence of any intercurrent event prior to Week 12, and the subject's last post baseline observation before the intercurrent event will be carried forward (LOCF) to impute missing endpoint value (for subjects whose postbaseline values are all missing, the baseline will be used to impute). Missing data at Week 12 will be imputed with LOCF method. Analysis of covariance (ANCOVA) models will be used to compare the change from baseline in DAS28-CRP at Week 12 for each of the KPL-404 dose groups and placebo. Baseline value and stratification factor will be included as covariates in the ANCOVA model. The least square (LS) mean of each treatment group, LS mean differences (each KPL-404 group vs. placebo), their standard errors and two-sided 95% CIs, and the nominal p-values for treatment differences will be obtained from the model. No testing between the two KPL-404 dose groups will be conducted.

Sensitivity Analysis (As-Observed Analysis)

The data collected after the intercurrent event will be included in the sensitivity analysis to evaluate the robustness of the primary analysis results with respect to the method of handling data while treatment discontinuation or taking the rescue medications (treatment policy strategy). In addition, for subjects discontinuing the study treatment before Week 12, their off-study treatment values measured up to Week 12 will be included in the analysis. There is no imputation for missing data at Week 12.

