For the sensitivity analysis of the primary efficacy endpoint, the observed data will be analyzed using a mixed model for repeated measures (MMRM) under the missing-at-random (MAR) assumption. Under this assumption, the efficacy outcome of subjects in each treatment group after early discontinuation will exhibit the same future evolution as subjects in the same group remaining in the study. The MMRM model will include fixed factors for treatment, visit, stratification factor, and treatment-by-visit interaction, and baseline DAS28-CRP as a covariate. An unstructured covariance matrix will be used to model the within-subject correlation. Kenward-Roger approximation will be used to calculate the denominator degrees of freedom. The LS mean, standard error, and LS mean treatment difference, along with the 95% CI and p-value will be provided.

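### The Cohort 3 ANCOVA and MMRM leave out the bDMARD vs JAKi factor that stratified subjects randomized under Amendment 3; the cost is at most a slightly conservative test

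*SAP*

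**What the plan says.** SAP 4.2.2 records that the stratification factor changed during the trial: "intolerance to RA medication category, bDMARD vs. JAKi) in Protocol Amendment 3 or earlier versions was changed to a new stratification factor", namely the number of advanced-therapy classes with inadequate response (≤1 vs ≥2), which applies from Amendment 4 on. It expects some subjects to have entered under the old scheme: "The modified CRF will collect such information for subjects in Cohorts 3 and 4 who are randomized under either Protocol Amendment 3" or the later amendments. Those under Amendment 3 can only be Cohort 3 subjects, because Cohort 4 first appears in protocol Version 6.0, which is Amendment 5 (Protocol Appendix 3; SAP Section 1).

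For these subjects, "The stratification will be derived per the information of prior inadequate response to RA medications for subjects who were randomized under Protocol Amendment 3", and the SAP adds "which will be reviewed in a blinded fashion before database lock". The factor listed for Cohorts 3 and 4 is class count alone. bDMARD vs JAKi is listed only for Cohorts 1 and 2.

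The current protocol (8.4) describes only the new scheme: "Randomization will be stratified by available documented evidence of prior inadequate response to ≤ 1 versus ≥ 2 classes of advanced targeted therapy". On the primary model, Protocol 11.4.2 says "Baseline and randomization stratification factor will be included as covariates in the ANCOVA model" and SAP 4.6.2 says "Baseline value and stratification factor will be included as covariates in the ANCOVA model". On the sensitivity model, SAP 4.6.2 says "The MMRM model will include fixed factors for treatment, visit, stratification factor, and treatment-by-visit interaction". Neither model names the old factor or the protocol version. The omission is read from 4.2.2, since 4.6.2 does not say which factor it means.

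**The concern.** Stratified randomization makes the arms alike on the stratifying factor. If that factor also predicts outcome, the treatment comparison becomes more precise, but the model reports the gain only if it contains the factor. When the factor is left out, its between-stratum variance stays in the residual. The printed standard error is then larger than the true sampling error, the confidence interval is too wide, and the test rejects less often than its nominal level.

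For the Amendment 3 part of Cohort 3, the derived class-count factor does not do this job, because it was not the factor balanced at their randomization. At stake is a little reported precision on the primary endpoint, in a cohort planned with 21 completers per arm.

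**Working it through.** **The plan's own figure.** SAP 1.5 assumes a difference of 1.2, SD 1.3, 21 completers per arm and two-sided 0.05. The two-sample t-test (noncentral t) gives 83.1%, against 83% stated. Allowing for 16% discontinuation, 21 / (1 − 0.16) = 25 per arm, as stated. The documents give no figure for the stratification question.

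**Inputs for the check**
- From the documents: 1:1:1 allocation, up to 25 per arm (75 in all), SD 1.3 (variance 1.69), effect 1.2. LOCF keeps nearly all subjects in the ANCOVA, so 25 per arm is used.
- Assumed, because the documents do not say: share f of Cohort 3 under Amendment 3, 33 to 67%; 30% in the JAKi stratum; outcome gap D between old strata, 0 to 1.0 point; old factor independent of class count; total SD held at 1.3; baseline covariate left out.

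**Formula.** The old factor contributes D² × 0.3 × 0.7 to the variance. Without it in the model, the reported SE is about √(2 × 1.69 / 25) = 0.368. Balance at randomization removes that contribution for the share f, so the true SE is about √(2 × (1.69 − f × 0.21 × D²) / 25).

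| f | D (points) | Reported SE | True SE | Overstated by |
|---|---|---|---|---|
| 33% or 67% | 0 | 0.368 | 0.368 | 0% |
| 33% | 0.5 | 0.368 | 0.366 | 0.5% |
| 67% | 0.5 | 0.368 | 0.364 | 1.1% |
| 33% | 1.0 | 0.368 | 0.360 | 2.1% |
| 67% | 1.0 | 0.368 | 0.352 | 4.4% |

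**Power in the last row.** The SAP model has 75 − 5 = 70 residual degrees of freedom (intercept, two treatment terms, baseline, class count). It rejects when the estimate exceeds 1.994 × 0.3677 = 0.733. Power is about Φ((1.2 − 0.733) / 0.3521) = Φ(1.33) = 90.8%. With the two extra terms (68 degrees of freedom), the limit is 1.995 × 0.3521 = 0.703, and power is about Φ((1.2 − 0.703) / 0.3521) = Φ(1.41) = 92.1%. The gain is about 1.4 points.

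**Simulation with 75 subjects**
- At f = 67% and D = 1.0, blocks of 3, 4,000 trials: without the old factor, empirical SE 0.351 and mean model SE 0.367 (0.367 / 0.351 = 1.046). With it, 0.350 and 0.351. The estimator's real precision hardly changes; what changes is whether the reported SE matches it.
- Power, 3,000 trials per scenario, blocks of 3 or 6: adding the old factor gains 0.1 to 0.5 points at D = 0.5, and about 1.5 points at f = 67% and D = 1.0 (89.7–89.8% to 91.2%).
- Over the whole assumed range, the SE is at most about 5% too large and the power gain is about 0 to 1.7 points.

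**Bias and type I error.** Runs with 63 completers, blocks of 6, f from 20 to 100% and a gap of 0, 0.5 or 1.0 SD put the SAP model's bias within about 0.01 point. Its type I error ran from 2.5 to 6.1%, with Monte Carlo SE about 0.4 points. The 6.1% arose with a gap of zero, where the omitted factor cannot matter, and the model containing that factor gave 5.7% in the same setting, so it is noise. The clear departures were downward: 3.2% at f = 80% and 2.5% at f = 100%, both with a 1.0 SD gap.

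**The case against.** The other side has a good deal. The change of factor is stated openly in SAP 4.2.2 and in the SAP's history of changes. The replacement is a characteristic fixed before randomization, reviewed blinded before lock. One definition across the cohort is a legitimate choice. The effect is small, may be zero, and runs in the conservative direction, in a Phase 2 study that reports nominal p-values. All of this stands, and it sets the priority low. It does not show that the old factor is in the model, and adding it costs almost nothing.

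Four stronger readings are tempting, and the documents do not support them.

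- **A breach of the protocol that SAP Section 6 should have listed.** Section 6 sets the SAP against Amendment 4, and by SAP 4.2.2 that amendment already used class count. In the current protocol, class count is the only stratification factor, so the covariate in Protocol 11.4.2 is most naturally read as that one. No Section 6 entry is missing.
- **A biased or anti-conservative comparison.** Neither appears in the checks.
- **A large power loss.** With 63 completers and a 1.0 SD gap, adding the old factor for everyone raised power by about 5 to 7 points. That gap is 1.3 points, more than the 1.2-point treatment effect. At f = 20%, most of the gain is ordinary covariate adjustment: 82.8% under the SAP model, 90.1% adjusting everyone, but only 83.7% using the strata as randomized.
- **A need to restratify the CMH.** With about 50 subjects per pairwise comparison, the Amendment 3 JAKi stratum would hold about 50 × 0.33 × 0.3 = 5 to 50 × 0.67 × 0.3 = 10 subjects. SAP 4.6.3 already falls back on an exact test when expected cells are below five, and the ACR endpoints would be adjusted for a different factor from the primary endpoint.

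**Conclusion.** The point holds as a modest gap in the linear models. For Cohort 3 subjects randomized under Amendment 3, the ANCOVA and MMRM adjust for a factor derived later and not for the one that balanced their allocation. The treatment estimate is unbiased and the type I error is not inflated. If bDMARD vs JAKi is prognostic, the model SE is about 0 to 5% too large, worth about 0 to 2 power points. If it is not prognostic, the effect is nil.

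These ranges rest on the assumed 33 to 67% share, 30% JAKi and 0 to 1.0 point gap. The documents give neither the number randomized under Amendment 3 nor the prognostic strength of the old factor. A larger share combined with a larger gap would raise the figures: at f = 80% and a 1.3-point gap, the model SE was 0.403 against an empirical 0.367, about 10% too large. Nothing in the documents suggests that combination. This is a free improvement, low priority.

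**What to change.** In SAP 4.6.2, state that the stratification factor for Cohort 3 is class count, and keep it. For Cohort 3 only, add to the ANCOVA and the MMRM an indicator for protocol version (Amendment 3 vs later) and bDMARD vs JAKi within Amendment 3. Report how many Cohort 3 subjects were randomized under each scheme. Settle the wording before unblinding.

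Leave the CMH strata in SAP 4.6.3 as planned. SAP Section 6 needs no entry for the change of factor.

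The cost is a few lines of SAP text and two of about 70 residual degrees of freedom. The old stratum should be recoverable from the randomization system, though the documents do not say so outright. Protocol 10.2.3 also has prior advanced therapies recorded with response.

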4.2.3. Medical History

The medical history is coded using Medical Dictionary for Regulatory Activities (MedDRA) of the version at database lock. The summary of medical history will be presented with number (%) by System Organ Class (SOC) and Preferred Term (PT) sorted by internationally agreed order of SOC and by the decreasing frequency of PT within SOC in the KPL-404 combined column. Each subject will be counted only once for each PT within a SOC. Similarly, for determination of MedDRA SOC incidences, subjects who experience multiple medical conditions under the same SOC will be counted only once for that SOC.

Medical history details as collected on the electronic case report form (eCRF) such as body system, description, the date of onset, stop date and the current status of the condition will be presented in a by-subject data listing.

4.3. Prior, Concomitant and Rescue Medications

All medications will be coded using the World Health Organization (WHO) Drug Dictionary of the version at database lock.

Prior medications are defined as medications that started before the first dose of study drug. Concomitant medications are defined as medications that (1) started before the first dose of study drug and continued into the treatment period, or (2) started on or after the date of the first dose of study drug. The number (%) of subjects who took prior and concomitant medications will be summarized on the anatomical class (ATC level 3) and PT.

The table for prior medications will be sorted by decreasing frequency of anatomic class followed by all PTs based on the overall incidence across treatment groups. In case of equal frequency regarding anatomical classes (respectively PTs), alphabetical order will be used.

The table for concomitant medications will be sorted by decreasing frequency of anatomic class followed by all PTs based on the incidence of the KPL-404 dose. In case of equal frequency regarding anatomical classes (respectively PTs), alphabetical order will be used.

If a subject develops RA flares requiring a rescue medication, the subject must discontinue IMP after informing the medical monitor. A table for these subjects taking RA rescue medications will be generated.

Similarly, a table of all prior RA therapies will be generated.

4.4. Protocol Deviations

A protocol deviation is defined as a change, divergence, or departure from the approved study design or procedures defined in the protocol. Important protocol deviations are a subset of protocol deviations that may significantly impact the completeness, accuracy, and/or reliability of study data or that may affect the subject's rights, safety, or well-being. All protocol deviations will be reviewed blindly before DBL.

Current ICH GCP guidelines request that the important protocol deviations must be listed in the clinical study report. These may include, but are not limited to:

- Subjects that are dosed on the study despite not satisfying the inclusion criteria.
- Subjects that develop withdrawal criteria whilst on the study but are not withdrawn.
- Subjects that receive the wrong treatment or an incorrect dose.

A summary table will be provided as the number (%) of subjects with at least one important protocol deviation and the number (%) of subjects in each category. The protocol deviation data will also be presented as a by-subject data listing.

4.5. Treatment Exposure and Compliance

The study medication administration details including the administration date and time, dose, and comments will be presented in a by-subject listing.

The following parameters related to study drug administration will be summarized with descriptive statistics by treatment group for the safety population:

- Treatment duration in weeks is defined as [(minimum of (date of last study drug +13, EOS) Day 1 + 1/7] for Cohorts 1 and 2
- Treatment duration in weeks is defined as below for Cohort 3:

- 5 mg/kg SC qwk group: [(minimum of (date of last study drug +6, EOS) Day 1 + 1)/7]
- o 5 mg/kg SC q2wk group:
 - If the last dose is 5 mg/kg, then [(minimum of (date of last study drug +13, EOS) Day 1 + 1)/7]
 - If the last dose is placebo, then [(minimum of (date of last study drug +6, EOS) Day 1 + 1)/7]
- O Placebo group: [(minimum of (date of last study drug +6, EOS) Day 1 + 1)/7]
- Treatment duration in weeks is defined as [(minimum of (date of last study drug +27, EOS) Day 1 + 1)/7] for Cohort 4
- Number of dose administrations (injections) received per subject will be summarized as 1 dose, 2 doses, 3 doses, 4 doses, 5 doses and 6 doses for Cohorts 1 and 2, up to 12 doses for Cohort 3, and up to 3 doses for Cohort 4. Treatment compliance is defined as the number of injections that the subject is actually received divided by the total number of injections that the subject is planned to take from the first injection of study medications up to the actual last injection of study medications. No imputation will be made for subjects with missing or incomplete data.

All study drug exposure data will be listed including reasons for dose not administered.

4.6. Analysis of Efficacy Endpoints

All efficacy analyses will be conducted by treatment group in the mITT population. The statistical analyses of the primary and secondary endpoints will be repeated in PP population. Analyses based on the mITT population will be the primary analyses and the analyses based on other populations will be considered as the supportive analyses.

Descriptive statistics will be provided for data in follow-up period by the treatment group, unless otherwise specified.

For Cohorts 1 and 2, descriptive statistics will be produced for all efficacy parameters. For the exploration of treatment effect, t-test and Fisher's exact test will be used for continuous endpoints and binary endpoints respectively.

For Cohorts 3 and 4, each endpoint will be analyzed following the details below.

4.6.1. Multiplicity Adjustment

As this is a phase 2 study, there is no multiplicity adjustment planned for the comparisons of multiple dose levels of KPL-404 versus placebo.

